### **3.2 Non-Compliance**

Subjects, who in the opinion of the investigator may not be able to comply with IL-2 or ECP treatment requirements or the safety monitoring requirements of the study, will be excluded from participation .

### **3.3 Inclusion of Women and Minorities**

The study is open to anyone regardless of gender or ethnicity. Efforts will be made to extend the accrual to a representative population, but in a trial that will accrue between 17-37 subjects, a balance must be struck between subject safety considerations and limitations on the number of individuals exposed to potentially toxic or ineffective treatments on the one hand and the need to explore gender, racial, and ethnic aspects of clinical research on the other. If differences in outcome that correlate to gender, racial, or ethnic identity are noted, accrual may be expanded or additional studies may be performed to investigate those differences more fully.

## **4.0 Screening and Registration Procedures**

---

### **4.1 Screening Procedures**

The following evaluations must be performed within four weeks prior to IL-2 +ECP treatment for all patients on protocol:

- Medical history and documentation of rationale for enrollment on IL-2 + ECP therapy on protocol.
- Physical examination, documentation of vital signs and KPS.
- Chronic GVHD assessment based on NIH consensus criteria – see Appendix C.
- Baseline lab work including CBC with differential, CMP and TSH/Vitamin D screen.
- Serum samples and mononuclear cells to be collected for immune assessment.
- Pregnancy test for women of childbearing age.
- Pulmonary function tests for patients with pulmonary manifestations of cGVHD.
- Dermatologic assessment for patients with cutaneous cGVHD.
- Flexion assessment of affected joints for individuals with contractures or musculoskeletal involvement secondary to cGVHD.

### **4.2 Informed Consent**

The investigational nature and objectives of the trial, the procedures and treatments involved and their attendant risks and discomforts, and potential alternative therapies will be carefully explained to the subject and a signed informed consent will be obtained. Documentation of informed consent for screening will be maintained in the subject's research chart and medical record.

### **4.3 Registration Requirements/Process**

Following informed consent, the patient will be registered through the Clinical Trials Office (CTO) prior to the initiation of therapy. Any participant not registered to the protocol before treatment begins will be considered ineligible and registration will be denied. A member of the study team will confirm eligibility criteria and complete the protocol-specific eligibility checklist.

[figure not shown]
Following registration, participants may begin protocol treatment. Issues that would cause treatment delays should be discussed with the Principal Investigator. If a participant does not receive protocol therapy following registration, notify the CTO of participant status changes as soon as possible.

#### 4.4 Randomization and/or Dose Level Assignment

NA. This is a phase II single-arm trial. There is no dose escalation or randomization.

### 5.0 Treatment Program

#### 5.1 Treatment Overview

GVHD and Immune Assessment and QOL will be performed at week 7 instead of week 6.

(NB: Patients deriving clinical benefit after initial 12 week therapy have the option to go on a maintenance phase .

#### 5.2 Treatment Schedule

##### 5.2.1 IL-2 Therapy

D. IL-2 will be self-administered by patients as a daily subcutaneous injection. Teaching will be provided before the first subcutaneous injection. The pharmacist, or the primary pharmacy technician working under the supervision of the pharmacist, will prepare the drug under aseptic conditions. The amount (in IU) of drug to be administered will be determined based on body surface area (BSA). The dose should be calculated based on body weight at screening, at a dose of  $1 \times 10^6$  IU/m^2/day for 12 weeks. All treatments will be outpatient based. If however, patients live within a 15 mile distance of the medical center and /or insurance mandates that the IL-2 be given in physician office- IL-2 injections will be given in the infusion center. After completion of 12 weeks of protocol therapy, responding patients will have the option of continuation of therapy till clinical benefit is no longer maintained. IL-2 will be provided by Prometheus Labs for this study. No protocol specific monitoring or follow up data will be collected after initial 12 week period. Monitoring of these patients will be according to acceptable standards of care for patients on cytokine therapy with IL-2. Ongoing responses will be monitored by the NIH consensus criteria guidelines , again off protocol . We hypothesize that maintenance therapy with IL-2 and ECP will

maintain elevated T reg: Tcon ratio, thereby translating into fewer clinical relapses and improved clinical outcomes.

### 5.2.2 ECP Therapy

ECP will be performed on an outpatient basis in the Amini Building at COH medical Campus according to the following schedule. All patients will have baseline evaluation in the cGVHD clinic prior to initiation of ECP.

- Weeks 1-4: twice weekly ECP
- Weeks 5-12: two ECP treatments every two weeks ( weeks 5,7,9 and 11)

ECP treatments will be preferably given on consecutive days of the week (eg Monday and Tuesday) however this is not always possible. Schedule will be determined based on availability of ECP in the Apheresis center.

### 5.2.3 Observations and Tests to be Performed

Patients will be evaluated for response to intervention (ECP + IL-2) at baseline and at weeks 37, 9, 12 and 16. NIH clinical scoring forms will be used to document responses. Markers of immune activation will be monitored at the same time points from blood samples taken on scheduled clinic visits. Quality of Life Assessments will also be performed at baseline and in weeks 7 and 12.

### 5.2.4 Documentation of compliance to therapy

Each participant will be given explicit instructions for taking IL-2 subcutaneous injections at home. Compliance to IL-2 home therapy will be closely monitored while they are on protocol therapy and patient will be given detailed instructions by the physician and research nurse in terms of administration of IL-2 subcutaneously and anticipated side effects. All enrolled patients will be given a drug diary (provided by the research nurse) at enrollment where they will document daily drug use and any missed doses and reasons thereof. The diary will be returned to the Research Nurse every 2 weeks while on protocol therapy and a new one will be issued at the same time.. IL-2 typically is supplied in  $22 \times 10^6$  units multidose vials and these will be individually dispensed in single dose syringes to enrolled patients every 2 weeks for home administration.

DO NOT ADMINISTER IL-2 AS INTRAVENOUS PUSH OR BOLUS.

Pre-medications are not required prior to the first dose or later doses.

All treatment including IL-2 administration and ECP procedures will be conducted in the outpatient setting, unless patient is hospitalized for some other medical condition unrelated to underlying hematologic disease or adverse effects of therapy (e.g. therapy will continue while inpatient for pain control, failure to thrive etc.). ICU admission, respiratory and hemodynamic compromise will be grounds for withholding therapy. See section 6.0 for dose modification and stoppage rules.

Prednisone (or equivalent steroid) will be continued concomitantly with IL-2 without dose modification. Taper of prednisone, or any other immune suppression medications, will not be permitted during the initial 6 weeks of the study, but can be reduced thereafter in responders at the discretion of the treating physician.

Of note, clinically stable cGVHD during taper of other immune suppression medications will be considered evidence of IL-2 efficacy; and progression of cGVHD during taper of other immunosuppressive therapy will not be considered evidence of IL-2 toxicity or lack of efficacy.

### **5.3 Planned Duration of Therapy:**

IL-2 and ECP combination therapy will be given for 12 weeks, with final immune assessment occurring at 16 weeks post-initiation of therapy. Patients deemed to be benefiting from combination therapy (i.e. in complete remission, partial remission, minor response or stable disease), will have the options to continue onto the extended duration per discretion of treating physician.

### **5.4 Optional Extended-duration therapy:**

As mentioned in the section above, patients who are responding to upfront therapy with IL-2 and ECP will be eligible to continue combination therapy with daily subQ IL-2 and ECP per SOP guidelines till clinical benefit is no longer maintained or toxicities develop. While on the optional maintenance therapy, these patients will be monitored for response and toxicity profile in the GVHD clinic on a monthly basis. This monitoring will not require data collection from research staff for response or adverse effect monitoring. Best clinical judgment will be used to determine on each monthly visit on rationale to continue commercial supply IL-2 or not based on clinical benefit and adverse effect profile of IL-2.

### **5.5 Criteria for Removal from Treatment**

- Subject withdraws consent
- Non-compliance
- Administrative reasons (insurance loss or no coverage of IL-2 or ECP by third party payors)
- Any Grade 4 non hematologic adverse event
- Life threatening anaphylactic reaction to IL-2
- Recurrent or non-resolving grade 3 toxic event
- Malignant relapse
- Clinical worsening of GVHD requiring the addition of a new immunosuppressive medication. A 50% increase in the corticosteroid dose will be considered evidence of worsening GVHD. Changes in other immunosuppressive medication doses to maintain a therapeutic level alone will not be criteria for removal from the trial.

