### 6.1 IL-2 Therapy

The dose modifications as described below are required for patients in the first 12 weeks of study and recommended but not mandatory for participants proceeding on extended duration therapy at the end of the 12-week study.

- Unexpected CTC Grade 3 toxicity: IL-2 will be withheld for unexpected non-hematologic toxicities that are grade 3. Expected IL-2 toxicities are listed in Section 8.1.3. If the toxicity resolves to grade 1 or below within 2 weeks, IL-2 can be restarted at a 50% reduced dose that will not be re-escalated. If the toxicity does not resolve in 2 weeks to grade 1 or below, or recurs to grade 3 or above after restarting IL-2, IL-2 will be discontinued.
- Expected non-hematologic toxicity: IL-2 can be withheld and/or restarted at a 50% reduced dose for less than grade 3 toxicity (e.g. local site reactions, persistent constitutional symptoms) in the interest of patient tolerability and at the discretion of the treating physician.
- Severe (grade-4) hematologic toxicity: IL-2 will be withheld for severe declines in peripheral counts (ANC<500, Plts<10,000) not related to malignant disease relapse, infection or other etiologies. If counts improve (ANC>1000, Plts>20,000) within 2 weeks, IL-2 will be restarted at a 50% reduced dose and not re-escalated. If peripheral counts do not improve within 2 weeks, or drop again (ANC<500, Plts<10,000) after restarting IL-2, it will be discontinued. Use of myeloid growth factors and transfusion of platelet and PRBC's will be per standard institutional guidelines and is allowed while patients are on trial.
- Infection: Of note, infection during IL-2 treatment is not considered IL-2 related, since both cGVHD and the concurrent use of immune suppression medications are known risk factors for infection. Infection is therefore considered an expected complication of cGVHD. However, patients who develop a CTC grade 3 or higher infection prior to week 12 of IL-2 therapy will have IL-2 withheld. They can be considered for restarting IL-2 at their prior dose after control of infection, at the discretion of the treating physician.
- Treatment Interruption: Within the first 12 weeks of IL-2 therapy, a  $\geq 6$ -week interruption will result in the participant being considered unevaluable for response (or lack thereof), unless objective improvement of cGVHD is documented with a shorter course of IL-2.

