### 6.2 Extracorporeal photopheresis:

The incidence of ECP reported side effects is extremely low at less than 0.003% especially in cGVHD patient population. The procedural risks with new third generation ECP devices is even smaller. Many of the complications attributable to ECP are related to vascular access. It would be preferable to use peripheral veins, but patients with cGVHD frequently have poor veins, and alternative access must therefore be used. When central venous catheters are used, complications such as infection, clotting in the catheters, deep venous thrombosis, and vessel stenosis can occur.

For this study, modifications of ECP therapy as described below are required for patients in the first 12 weeks of study. Infection: Of note, infection during ECP+ IL-2 treatment is not considered intervention-related, since both cGVHD and the concurrent use of immune suppression medications are known risk

factors for infection. Infection is therefore considered an expected complication of cGVHD. However, patients who develop a CTC grade 3 or higher infection prior to week 12 of ECP+ IL-2 therapy will have therapy withheld during active infection. They can be considered for restarting ECP after control of infection, at the discretion of the treating physician. CVP line infection and bacteremia/sepsis requiring line removal will result in temporary stoppage of ECP therapy.

- Severe (grade-4) hematologic toxicity: ECP+IL-2 will be withheld for severe declines in peripheral counts (ANC<500, Plts<10,000) not related to malignant disease relapse, infection or other etiologies. If counts improve (ANC>1000, Plts>20,000) within 2 weeks, ECP will be restarted per schedule. If peripheral counts do not improve within 2 weeks, or drop again (ANC<500, Plts<10,000) after restarting ECP + IL-2, it will be discontinued. Use of myeloid growth factors and transfusion of platelet and PRBC's will be per standard institutional guidelines and is allowed while patients are on trial.

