### **Adverse Events and Serious Adverse Events**

The PI will be responsible for determining the event name, assessing the severity (i.e., grade), expectedness, and attribution of all adverse events.

**Adverse Event (AE)** - An adverse event is any untoward medical experience or change of an existing condition that occurs during or after treatment, whether or not it is considered to be related to the protocol intervention.

**Reporting** - Participating investigators will assess the occurrence of AEs and SAEs at all participant evaluation time points during the study. All CTC grade 3 or higher AEs and all SAEs whether reported by the participant, discovered during questioning, directly observed, or detected by physical examination, laboratory test or other means, will be recorded in the participant's medical record and on the appropriate study-specific case report forms from day 1 of treatment until 30 days after the last IL-2 injection.

The descriptions and grading scales found in the CTEP Version 4.0 of the NCI Common Terminology Criteria for Adverse Events (CTCAE) will be utilized for AE reporting. The CTEP Version 4.0 of the CTCAE is identified and located on the CTEP website at:

[https://ctep.cancer.gov/protocolDevelopment/electronic\\_applications/ctc.htm](https://ctep.cancer.gov/protocolDevelopment/electronic_applications/ctc.htm)

**Reporting Non-serious Adverse Events** – Adverse events will be collected after the patient is given the study treatment or any study related procedures. Adverse events will be monitored by the PMT. Adverse events that do not meet the criteria of serious OR are not unanticipated problems will be reported only in the PMT Report.

**Serious Adverse Event (SAE)** [Modified from the definition of unexpected adverse drug experience in [21 CFR 312.32](#)] - defined as *any expected or unexpected adverse events* that result in any of the following outcomes:

- Death
- Is life-threatening experience (places the subject at immediate risk of death from the event as it occurred)
- Unplanned hospitalization (equal to or greater than 24 hours) or prolongation of existing hospitalization
- A persistent or significant disability/incapacity
- A congenital anomaly/birth defect
- Secondary malignancy

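### A grade 4 infection before week 12 means removal from treatment under section 5.5, but sections 6.1 and 6.2 allow IL-2 and ECP to restart, and no text says which section governs

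*Combined protocol and SAP*

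**What the plan says.** Section 5.5 (Criteria for Removal from Treatment) includes "Any Grade 4 non hematologic adverse event". It does not exempt infection or ask whether the event is related to treatment. Section 7, under Adverse Events and Serious Adverse Events, counts an untoward event as an adverse event "whether or not it is considered to be related to the protocol intervention".

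Section 6.1 gives infection its own rule for IL-2: "patients who develop a CTC grade 3 or higher infection prior to week 12 of IL-2 therapy will have IL-2 withheld". It goes on: "They can be considered for restarting IL-2 at their prior dose after control of infection, at the discretion of the treating physician". The opening of 6.1 makes its rules mandatory during the first 12 weeks.

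Section 6.2 does the same for ECP: "patients who develop a CTC grade 3 or higher infection prior to week 12 of ECP+ IL-2 therapy will have therapy withheld during active infection", followed by "They can be considered for restarting ECP after control of infection, at the discretion of the treating physician".

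Both 6.1 and 6.2 state that infection is regarded as a complication of cGVHD and its immunosuppression, not as related to the intervention. Neither refers to 5.5, and 5.5 does not refer to section 6.

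**The concern.** A grade 4 infection is a non-hematologic adverse event, so 5.5 takes the patient off treatment. The same event is an infection of grade 3 or higher, so 6.1 and 6.2 hold treatment and leave a restart open. A restart that section 6 permits is one that 5.5 rules out.

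The first stake is patient safety: whether someone may be re-exposed after a grade 4 infection depends on which page the physician consults. The second is data quality. Two otherwise identical patients could differ in:

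- IL-2 and ECP exposure before the week 12 assessment;
- the recorded off-treatment date and reason;
- the adverse event recording window in section 7, which ends 30 days after the last IL-2 injection;
- the timing of the final steroid and immune assessments, which section 11.2 sets at week 16 or 4 weeks after treatment ends.

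Following either section could also be logged as a deviation from the other.

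**Working it through.** The contradiction is textual and depends on no rate. Setting the rules side by side for a grade 4 infection before week 12:

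| Question | Section 5.5 | Sections 6.1 and 6.2 |
|---|---|---|
| Is the event covered? | Yes: grade 4, non-hematologic | Yes: grade 3 or higher, no upper limit |
| Does relatedness matter? | No, by the section 7 definition | Infection is deemed unrelated, but the rule still applies |
| Consequence | Removal from treatment | Withhold; restart may be considered |
| May IL-2 resume? | No | Yes, at the prior dose, if the physician decides |
| May ECP resume? | No | Yes, if the physician decides |
| Reference to the other rule? | None | None |

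**Is there an order of precedence?** Section 5.2.4 sends the reader to section 6.0 for modification and stoppage rules. It does not mention 5.5 or rank the two.

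**Does the drafting imply an exception?** Section 5.5 confines its grade 4 criterion to non-hematologic events, which fits the separate hold-and-restart rule for grade 4 hematologic toxicity in 6.1 and 6.2. The bullets there on unexpected non-hematologic toxicity are triggered at grade 3, leaving grade 4 to 5.5. Infection is the only non-hematologic event for which those sections give a hold-and-restart rule whose stated grade range reaches grade 4, and 5.5 has no matching carve-out.

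**Is the primary analysis affected?** Section 13.1 counts every eligible patient with a baseline assessment who receives protocol treatment of any duration. On that definition the patient is in the denominator under either rule.

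**How often might it arise?** The documents give no rate for this combination, so the following is illustrative.

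- Input: in the phase I trial of low-dose IL-2, 28 patients were evaluable for toxicity and one grade IV infection (MRSA pneumonia) was reported (section 2.4.1.2). Planned enrolment here is 24 (section 13.1).
- Point estimate: 1/28 = 3.6%; 24 × 1/28 = 0.86 patients expected.
- Exact (Clopper-Pearson) 95% interval for 1/28: 0.09% to 18.3%. The lower limit is 1 − 0.975^(1/28) = 0.0009. The upper limit solves (1 − p)^28 + 28p(1 − p)^27 = 0.025.
- Expected number in 24 patients: 24 × 0.0009 = 0.02 to 24 × 0.183 = 4.4.
- Chance of at least one: 1 − (27/28)^24 = 58% at the point estimate, and about 2% to 99% across the interval.

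**The case against.** The strongest reply is that the rules can be obeyed together. Sections 6.1 and 6.2 compel only withholding; restart is optional. A physician who withholds and never restarts satisfies all three sections. That is correct, and it means these are not two opposed mandates. It does not remove the conflict, because section 6 still grants a permission that 5.5 takes away.

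A second reply is that a specific infection rule naturally overrides a general list. That reading is possible, but no text adopts it. The statement that infection is not treatment-related does not help either, since the grade 4 criterion in 5.5 does not turn on attribution.

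Several stronger readings are tempting and should be resisted:

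- *Recurrent grade 3 infection is a second contradiction.* Section 5.5 also removes for a "Recurrent or non-resolving grade 3 toxic event". That wording differs from the adverse event term used for grade 4. Sections 11.2 and 13.1 tie consequential toxicity to treatment, while 6.1 and 6.2 deem infection unrelated. The phrase can therefore be read to leave infection out. This is an ambiguity, not a demonstrated conflict.
- *Section 5.2.4 independently contradicts 5.5.* It says "ICU admission, respiratory and hemodynamic compromise will be grounds for withholding therapy". It does not say that withholding is the only consequence, it points on to section 6.0, and ICU admission is not a toxicity grade.
- *Every serious infection is affected.* A first grade 3 infection that resolves meets no grade 4 criterion in 5.5, so it creates no conflict. The 18.4% infection figure for the randomized ECP arm (sections 2.1.2 and 2.4.2.2) has no stated grade and cannot be used to count cases.

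**Conclusion.** The conflict holds, and it is narrow: grade 4 infection before week 12. For that event one section requires removal, two others permit re-treatment, and nothing ranks them. This rests only on the wording of 5.5, 6.1, 6.2 and the section 7 definition.

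The event is plausible, but its frequency is barely known. The figure of about 0.9 expected patients in 24 (range roughly 0.02 to 4.4) comes from a single event, pooled over three IL-2 dose levels in an 8-week course without ECP. It assumes that this rate carries over to 12 weeks of the combination. The 58% chance of at least one case should not be quoted without its range of about 2% to 99%.

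A reader might infer that the primary result is compromised. The documents do not support that: the section 13.1 denominator is the same under either rule, and no effect on the Simon decision rule or the toxicity stopping boundary has been shown. The point merits correction because it governs re-treatment after a grade 4 event and makes exposure and off-treatment data depend on the section followed.

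**What to change.** Reconcile sections 5.5, 6.1 and 6.2 so that a grade 4 infection before week 12 has one stated consequence for IL-2 and for ECP. Add a cross-reference in each place and a statement of which section governs. This can be done by having 5.5 address infection explicitly, or by having the infection text in 6.1 and 6.2 state how it relates to the grade 4 criterion. Which clinical rule applies is for the sponsor to decide.

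As a secondary clarification, state whether the grade 3 toxic-event criterion in 5.5 includes infection.

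The cost is one or two sentences in an amendment, with no new procedures, visits or patients.
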